		Proportion of patients with SJC = 0 for patients with current or historical peripheral arthritis at Baseline	Analysis of SJC = 0 only applies to patients with current or historical peripheral arthritis at Baseline	Missing if observed value is missing

Measure	Description	Variable	Derivation / Comment	Imputation Approach if with Missing Components
Anterior Uveitis	At each study visit, study health care providers will evaluate the patient for any symptoms of anterior uveitis.	Incidence and incidence rate of anterior uveitis	Anterior uveitis will be summarized for patients with or without prior anterior uveitis, separately.  Anterior uveitis is identified using the preferred term “iridocyclitis”.	Not applicable (NA)
Non-Steroidal Anti-Inflammatory Drug (NSAID) Intake	Information regarding NSAIDs (including COX-2 inhibitors) intake will be collected in the eCRF and the ASAS-NSAID score will be calculated (Dougados et al. 2011).	Proportion of patients taking NSAID	Proportion of patients taking NSAID (including COX-2 inhibitor) at specified visit	NA
		ASAS - NSAID score	See Section 6.10.4.1 and Appendix 5 for details of deriving ASAS-NSAID score. ASAS-NSAID = 0 if no NSAID use	If NSAID dose is missing, the maximum efficacy dose (Appendix 5) is assumed. If frequency is missing, ‘every day’ intake is assumed. If start/stop dates are missing, follow missing date rule in Section 6.9.2
		ASAS-NSAID score change from baseline	Calculated as: observed ASAS-NSAID score – baseline ASAS-NSAID score	
		ASAS-NSAID50	$100 \times \frac{\text{Baseline ASAS} - \text{NSAID} - \text{Observed ASAS} - \text{NSAID}}{\text{Baseline ASAS} - \text{NSAID}}$ Proportion of patients with at least 50% decrease from baseline in ASAS-NSAID score. Derivation only applies to patients whose ASAS-NSAID is not equal to 0 at baseline.	

Measure	Description	Variable	Derivation / Comment	Imputation Approach if with Missing Components
MRI Sacroiliac Joint (SIJ) (Spondyloarthritis Research Consortium of Canada [SPARCC] Score)	Both left and right SIJ are scored for bone marrow edema. Each side has 6 slices and each slice has 6 scoring units, score of 0 or 1. Total SIJ SPARCC scores can range from 0 to 72 with higher scores reflecting worse disease. Scoring will be performed by a central reader.	SPARCC SIJ Score	The SPARCC SIJ Score is sum of 72 scoring units; the sum ranges from 0 to 72.	See “MRI Data Programming Guidance for AxSpA Studies’ for missing rule and imputation method.
		SPARCC SIJ change from baseline – major secondary outcome (Week 16 only)	Calculated as: observed SPARCC SIJ – baseline SPARCC SIJ	Missing if baseline or observed value is missing
Spondyloarthritis Research Consortium of Canada –SIJ Structure Score (SSS)	Structural lesions in MRIs of the SIJ are assessed using the SPARCC SSS method for both left and right side. Each site has 5 slices. For fat metaplasia and bone erosion,	SPARCC SIJ SSS Score	For each feature, sum all corresponding scoring units. The sum ranges are fat metaplasia (0 to 40), erosions (0 to 40), backfill (0 to 20), and ankylosis (0 to 20)	See “MRI Data Programming Guidance for AxSpA Studies’ for missing rule and imputation method.

Measure	Description	Variable	Derivation / Comment	Imputation Approach if with Missing Components
	each slice has 1 scoring unit in each of the 4 quadrants; for backfill and ankyloses, each slice has 1 scoring unit in each of the upper and lower half. Each scoring unit has score of 0 or 1. (Maksymowych et al. 2015). Scoring will be performed by central readers.	SPARCC SIJ SSS change from baseline	Calculated as: observed SPARCC SIJ SSS – baseline SPARCC SIJ SSS	Missing if baseline or observed value is missing

Abbreviations: MRI = magnetic resonance imaging; no. = number; NRS = numeric rating scale; Q = question; rad-axSpA = radiographic axial spondyloarthritis; V = visit.

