### *NSAIDs and Analgesics:*

NSAIDs, including COX-2 inhibitors, will be allowed up to the maximum recommended doses for pain. Patients must be on a stable dose of NSAIDs/COX-2 inhibitors for at least 2 weeks prior to baseline randomization. Introduction of a new NSAID or dose adjustment to an existing NSAID is not permitted, unless required for safety reasons (AE).

Short-acting analgesics with no anti-inflammatory action (such as paracetamol) are permitted. If administered ad hoc as needed, they are to be withheld within the 24-hour period prior to any

assessment. Aspirin (in a dose not exceeding 350 mg/day) may be taken to manage cardiovascular risk.

Opiate analgesic use is allowed but is not to exceed an average daily dose of 30 mg/day of morphine or its equivalent. Introduction of a new opiate analgesic or dose adjustment to an existing opiate analgesic is not permitted, unless required for safety reasons or as premedication for MRIs.

*Conventional DMARDs:*

Discontinuation of excluded oral or injectable cDMARDs before study enrollment must occur at least 4 weeks prior to baseline. MTX (oral or parenteral up to 25 mg/week), sulfasalazine (up to 3 g/day), or hydroxychloroquine (up to 400 mg/day) may be allowed IF at stable dose for at least 4 weeks prior to baseline randomization. These agents can only be used as single agent therapy and not in combination with other cDMARDs. If, at any time, the investigator believes that side effects or laboratory abnormalities may be attributable to the cDMARD, then cDMARD dose is to be lowered or the medication stopped. Local standard of care is to be followed for concomitant administration of folic or folinic acid if MTX is taken.

*Corticosteroids:*

*Oral corticosteroids:* If on oral corticosteroids, the dose must not exceed 10 mg/day of prednisone or its equivalent and must be stable for at least 4 weeks prior to baseline randomization. Treatment alteration in oral corticosteroid dose is not to occur prior to Week 16.

*Parenteral corticosteroids (intravenous, intramuscular, intra-articular):* Treatment with any parenteral corticosteroids is not permitted within 6 weeks prior to baseline or up to Week 16.

*Inhaled and topical steroids:* Regular use of inhaled or topical steroids will be permitted during any study period.

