### **6.8.2. Concomitant Medications at or after Week 16 for Treatment Modifications (after Completion of Week 16 Assessments)**

*General:*

Changes in therapy are discouraged in the last 8 weeks prior to 52 week assessments.

*NSAIDs and Analgesics:*

Alterations of NSAIDs, including COX-2 inhibitors (dose change, introduction, or withdrawal), are allowed. Doses are recommended to be stable in the 2 weeks prior to an assessment. Any changes in frequency and/or dose must be recorded in the eCRF.

Short-acting analgesics with no anti-inflammatory action (such as paracetamol) are permitted. If administered ad hoc as needed, they are to be withheld within the 24-hour period prior to any assessment. Aspirin (dose not exceeding 350 mg/day) may be taken to manage cardiovascular risk.

Opiate analgesic use: Use of variable doses of opiate analgesics is allowed but is not to exceed an average daily dose of 30 mg morphine or its equivalent.

*Conventional DMARDs:*

Adjustment of allowed cDMARDs (eg, dose change, introduction, withdrawal of cDMARDs, or replacement of a current cDMARD with the introduction of a new cDMARD) is allowed after all assessments at Week 16 are completed. Not more than 1 adjustment of cDMARDs at 1 time within 8 weeks is recommended. cDMARD can only be used as a single agent and not in combination with other cDMARDs. Any changes must be recorded in the eCRF.

For all study periods, the maximum allowed dose is 25 mg/week for MTX, 3 g/day for sulfasalazine, and 400 mg/day for hydroxychloroquine. Local standard of care is to be followed for concomitant administration of folic or folinic acid if MTX is taken and for administration of other cDMARDs.

*Oral corticosteroids:* As of Week 16, adjustments of oral corticosteroids are allowed; however, the maximum dose is not to exceed 10 mg/day of prednisone or its equivalent at any time during these periods.

*Parenteral corticosteroids (intravenous, intramuscular, intra-articular):* As of Week 16, intra-articular injection of corticosteroid may be allowed, as needed. The joint injected must be designated along with the medication in the eCRF and must be recorded as unevaluable on the TJC/SJC assessment.

*Inhaled and topical steroids:* Regular use of inhaled or topical steroids will be permitted during any study period.

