#### **8.1.2.12. Peripheral Arthritis**

##### **8.1.2.12.1. Tender Joint Count**

The number of tender and painful joints will be determined by examination of 46 joints (23 joints on each side of the patient’s body). The 46 joints to be assessed and classified as tender or not tender are detailed in site training materials. Any joints that require intra-articular injections

during the study (according to Section 6.8) must be excluded from evaluation from the time of the injection to the conclusion of the study.

Joint assessments will be performed by an experienced rheumatologist or skilled and trained assessor. To minimize interobserver variation, particularly during the Blinded Treatment Dosing Period (Period 2), it is recommended that the same assessor performs the TJC for a given patient. Missing, replaced, ankylosed, or arthrodesed joints will be identified by the investigator at the Screening Visit and will be excluded from evaluation during the study.

The TJC data will be collected electronically.

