Section 6.17 Interim Analyses and Data Monitoring	Removed the data review committee and data monitoring committee meeting as they were not happened prior to W52 lock.

Section	Revision
Section 6.18	Fatigue NRS psychometric analyses were removed
Section 6.18.1	The empirical cumulative distribution function (eCDF) and probability density function (PDF) plots for change in ASAS HI from baseline to Week 16 (mBOCF) by the selected anchors and treatment group (including placebo) were added ROC analysis was removed
Section 6.18.2	The empirical cumulative distribution function (eCDF) and probability density function (PDF) plots for change in SF-36 from baseline to Week 16 (mBOCF) by the selected anchors and treatment group (including placebo) was added.
Appendix 4	Removed the non-evaluable joint imputation
Appendix 6	Updated to use version of '2009 general US population'; Added to include norm-based score for SF-36 domain; Updated to include incomplete records into the CSV file and allow software to handle the item=level missing within the software.
Appendices 7-11	Updated relevant AE terms per most recent PSAP
Appendix 12, 13	Added ATC codes/terms for drug of special interest; medical guidance on clinically meaningful change

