### 6.3.1. Nonresponder Imputation

Analysis of categorical efficacy and health outcome variables will be assessed using a nonresponder imputation (NRI) method. Patients will be considered nonresponders for the NRI analysis if they do not meet the clinical response criteria or have missing clinical response data at the primary analysis time points. All nonresponders at Week 16 (Visit 8), as well as all patients who discontinue study treatment at any time prior to Week 16 for any reason, will be defined as nonresponders for the NRI analysis at Week 16. Similarly, all nonresponders at Week 52 (Visit 15), as well as patients who discontinue study treatment at any time prior to Week 52 for any reason, will be defined as nonresponders for the NRI analysis at Week 52. Patients who are deemed as inadequate responders by the investigator on or after Week 16 but remain on initially assigned blinded study treatment and only have modifications in concomitant medications will not influence whether or not a patient would be considered a nonresponder. Patients who stopped originally assigned blinded study treatment and use rescue ixekizumab 80 mg Q2W will be analyzed as nonresponders for the Week 52 analysis. They will be considered as nonresponders after the time of initiation of biologic rescue of ixekizumab 80 mg Q2W.

Randomized patients without at least 1 postbaseline observation will also be defined as nonresponders for the NRI analysis.

The NRI may be applied at any time point specified for analysis.

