		SPARCC enthesitis score = 0	SPARCC enthesitis score = 0 refers to complete resolution in enthesitis. Analysis of SPARCC enthesitis score = 0 only applies to patients with baseline enthesitis (SPARCC enthesitis >0).	Missing if observed value is missing
Tender Joint Count (TJC)	The number of tender and painful joints will be determined by examination of 46 joints (23 joints on each side of the patient’s body). The 46 joints are assessed and classified as tender or not tender.	TJC total score	Adjusted sum of the pain/tenderness for all 46 joints: $\left( \frac{\text{sum of all joints checked to be painful/tender}}{\text{number of evaluable joints}} \right) \times 46$ See Appendix 4 for details.	If more than half of the joint scores are non-evaluable, the total score will be missing.
		TJC change from baseline	Calculated as: observed TJC – baseline TJC only applies to patients whose baseline TJC >0.	Missing if baseline or observed value is missing
		Proportion of patients with TJC = 0 when baseline TJC > 0	Analysis of TJC = 0 only applies to patients whose baseline TJC > 0.	Missing if observed value is missing

Measure	Description	Variable	Derivation / Comment	Imputation Approach if with Missing Components
		Proportion of patients with TJC = 0 for patients with current or historical peripheral arthritis at baseline	Analysis of TJC = 0 only applies to patients with current or historical peripheral arthritis at baseline	Missing if observed value is missing
Swollen Joint Count (SJC)	The number of swollen joints will be determined by examination of 44 joints (22 joints on each side of the patient’s body). The 44 joints are assessed and classified as swollen or not swollen.	SJC total score	Adjusted sum of the pain/tenderness for all 44 joints. $\left( \frac{\text{sum of all joints checked to be swollen}}{\text{number of evaluable joints}} \right) \times 44$ See Appendix 4 for details.	If more than half of the joint scores are nonevaluable, the total score will be missing.
		SJC change from baseline	Calculated as: observed SJC – baseline SJC Only applies to patients whose baseline SJC >0.	Missing if baseline or observed value is missing
		Proportion of patients with SJC = 0 when baseline SJC > 0	Analysis of SJC = 0 only applies to patients whose baseline SJC > 0.	Missing if observed value is missing

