Enthesitis Scores	MASSES and SPARCC change from baseline	MMRM	ITT Population with Baseline MASSES >0 (or SPARCC >0)	IXE80Q2W & IXE80Q4W vs. placebo at Weeks 16 and 52 and all other postbaseline visits in Period 2	Other secondary efficacy analyses (Section 6.10.4).
		ANCOVA with mBOCF	ITT Population with Baseline MASSES >0 (or SPARCC >0)	IXE80Q2W & IXE80Q4W vs. placebo at Weeks 16 and 52 and all other postbaseline visits in Period 2	Other secondary efficacy analyses (Section 6.10.4).

Measure	Variable	Analysis Method (Sections 6.1 and 6.3)	Population (Section 6.1.1)	Comparison/Time Point	Analysis Type
		ANCOVA with mBOCF	ITT Population with Current or Historical Enthesitis at Baseline	IXE80Q2W & IXE80Q4W vs. placebo at Weeks 16 and 52 and all other postbaseline visits in Period 2	Other secondary efficacy analyses (Section 6.10.4).
	MASES score = 0 (similarly SPARCC = 0)	Logistic regression analysis with NRI; Fisher's exact test with NRI	ITT Population with Baseline MASES >0 (or SPARCC >0)	IXE80Q2W & IXE80Q4W vs. placebo at Weeks 16 and 52 and all other postbaseline visits in Period 2	Other secondary efficacy analyses (Section 6.10.4).
		Logistic regression analysis with NRI; Fisher's exact test with NRI	ITT Population with Current or Historical Enthesitis at Baseline	IXE80Q2W & IXE80Q4W vs. placebo at Weeks 16 and 52 and all other postbaseline visits in Period 2	Other secondary efficacy analyses (Section 6.10.4).
Peripheral Arthritis	TJC and SJC change from baseline	MMRM	ITT Population with baseline TJC >0 (or SJC >0)	IXE80Q2W & IXE80Q4W vs. placebo at Weeks 16 and 52 and all other postbaseline visits in Period 2	Other secondary efficacy analyses (Section 6.10.4).
		ANCOVA with mBOCF	ITT Population with baseline TJC >0 (or SJC>0)	IXE80Q2W & IXE80Q4W vs. placebo at Weeks 16 and 52 and all other postbaseline visits in Period 2	Other secondary efficacy analyses (Section 6.10.4).
		ANCOVA with mBOCF	ITT Population with Current or Historical Enthesitis at Baseline	IXE80Q2W & IXE80Q4W vs. placebo at Weeks 16 and 52 and all other postbaseline visits in Period 2	Other secondary efficacy analyses (Section 6.10.4).
	TJC = 0 when baseline TJC > 0 (similarly SJC = 0 when baseline SJC > 0)	Logistic regression analysis with NRI; Fisher's exact test with NRI	ITT Population with Baseline TJC>0 (or SJC>0)	IXE80Q2W & IXE80Q4W vs. placebo at Weeks 16 and 52 and all other postbaseline visits in Period 2	Other secondary efficacy analyses (Section 6.10.4).

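### After Week 16, a joint given an intra-articular steroid injection leaves the tender and swollen joint counts for good, so a patient whose remaining active joints have all been injected is scored as a TJC = 0 or SJC = 0 responder

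*SAP*

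**What the plan says.** Protocol 6.8.1 bars injections in the first period: "Treatment with any parenteral corticosteroids is not permitted within 6 weeks prior to baseline or up to Week 16". Protocol 6.8.2, which applies once the Week 16 assessments are done, lifts the bar: "As of Week 16, intra-articular injection of corticosteroid may be allowed, as needed". The injected joint and the drug go into the eCRF, and the joint "must be recorded as unevaluable on the TJC/SJC assessment". Protocol 8.1.2.12.1 (tender joints) adds that such a joint "must be excluded from evaluation from the time of the injection to the conclusion of the study". Protocol 8.1.2.12.2 says the same for swollen joints.

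SAP Table RHBX.6.4 defines each count as the number of active joints over the number of evaluable joints, multiplied by 46 (TJC) or 44 (SJC). It refers to Appendix 4 for details, and its only missing-score rule is "If more than half of the joint scores are non-evaluable, the total score will be missing". The revision history entry for Appendix 4 reads "Removed the non-evaluable joint imputation".

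SAP Table RHBX.6.5 compares each ixekizumab arm with placebo on "TJC = 0 when baseline TJC > 0 (similarly SJC = 0 when baseline SJC > 0" by logistic regression and Fisher's exact test with nonresponder imputation (NRI). It repeats this in patients with current or past peripheral arthritis, and also analyses change in TJC and SJC. SAP 6.3.1 states that patients who stay on assigned treatment and "only have modifications in concomitant medications will not influence whether or not a patient would be considered a nonresponder".

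**The concern.** Proration over evaluable joints is reasonable for a joint that was never countable, such as one replaced before screening, because it is absent at baseline and at follow-up alike. An injected joint differs. It was counted at baseline and is then removed by a post-randomization event that is itself a likely sign of active disease in that joint. Proration gives it the average status of the joints that were not injected. When those are all quiet, that average is zero.

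The endpoint then records success for a patient whose affected joint nobody examines again. At stake is the meaning of the peripheral arthritis results after Week 16. Some responders could owe their status to the injection rather than to the randomized treatment, and the change scores could include falls that no joint examination supports.

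**Working it through.** The plan states no figure to reproduce here; the check applies its own formula.

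**Inputs**
- 46 joints for TJC and 44 for SJC (Protocol 8.1.2.12; SAP Table RHBX.6.4).
- Score = active joints / evaluable joints x 46 or 44, missing only if more than half are nonevaluable (SAP Table RHBX.6.4). A score is therefore still computed with up to 23 of 46, or 22 of 44, joints nonevaluable.
- Counts after Week 16 at Weeks 24, 36 and 52, and at early termination (Protocol Appendix 2).
- NRI triggers: criteria not met, response missing, study treatment stopped, or ixekizumab rescue (SAP 6.3.1).

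**Scores after injection, with all joints evaluable beforehand and no true change in any joint**

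| Active joints | Injected | TJC | SJC | Counted as responder |
|---|---|---|---|---|
| 1 | 1 | 0/45 x 46 = 0 | 0/43 x 44 = 0 | yes |
| 2 | 1 | 1/45 x 46 = 1.02 | 1/43 x 44 = 1.02 | no |
| 2 | 2 | 0 | 0 | yes |
| 3 | 2 | 1/44 x 46 = 1.05 | 1/42 x 44 = 1.05 | no |

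A false zero therefore requires every remaining active joint to have been injected.

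**Change from baseline.** Baseline TJC 4, nothing improves, one tender joint injected: 3/45 x 46 = 3.07. The change is 3.07 - 4 = -0.93, which is 0.93/4 = 23% of baseline.

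**Does another rule catch it?**
- The missing-score rule does not, because one or a few injected joints are far below half.
- NRI does not: the score is present, and a change in concomitant medication alone is not a trigger. Patients who move to ixekizumab rescue are already nonresponders, so only those on assigned treatment are exposed.
- mBOCF acts on study-drug discontinuation or ixekizumab rescue (SAP 6.3.2), not on injections.
- The per-protocol set is used only for ASAS40 (SAP Table RHBX.6.1). Placebo multiple imputation and the tipping-point analysis cover only ASAS40 and ASDAS (SAP 6.3.4, 6.3.5).

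**Illustrative size.** The documents do not say how many patients per arm have baseline SJC above 0. Assuming 20 to 40, one converted patient moves that arm's SJC = 0 rate by 1/20 = 5.0 to 1/40 = 2.5 percentage points. This is the weight of one patient, not an estimate of bias.

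**The case against.** The best defence is that Table RHBX.6.4 defers to Appendix 4, whose text is redacted, so a special rule for injected joints cannot be excluded. That stands as a limit on certainty. The only visible statement about that appendix, however, is that an imputation for non-evaluable joints was taken out.

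A second defence is that both documents deliberately keep changes in concomitant medication from deciding response, so an exception for injections is a choice of estimand. This stands in part: the fix does depart from the general rule for two endpoints. But counting whatever is observed after a medication change presupposes an observation, and here the joint is no longer examined.

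Third, the reach is small. These are other secondary endpoints without multiplicity adjustment (SAP 6.10.4), injections planned at entry are excluded (criterion 34), and therapy changes are discouraged in the last 8 weeks before Week 52. All of this stands. The concomitant therapy summaries compare medication use between arms and might show an imbalance, but they would not identify which responders arose through an injected joint.

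A reader might also infer more than the documents support:
- That any injection creates a responder. The table above shows it does not.
- That all visits from Week 20 are affected. Joint counts are not scheduled at Weeks 20, 28, 32 or 44.
- That the SAP describes a zero joint count as full resolution. It uses such a label only for the enthesitis scores.
- That the rule favours ixekizumab. If injections were more frequent on placebo, the false responders would fall there and the drug effect would be understated.

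**Conclusion.** On the visible text the rules combine to give a wrong result. After the Week 16 assessments, a patient who stays on assigned treatment and whose remaining active joints have all been injected is scored TJC = 0 or SJC = 0 whatever those joints do later. When only some active joints are injected, the count is biased downward. The exposed counts are Weeks 24, 36 and 52, or early termination.

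Week 16 is unaffected because the protocol does not permit injections before then. ASAS40 and the major secondary endpoints are unaffected because none of them uses an examined joint count. The conclusion rests on the redacted Appendix 4 containing no rule for injected joints. The size and direction of any between-arm bias cannot be computed, since the documents give neither an injection frequency nor the number of patients with active joints at baseline. The change is worth making, but it does not bear on the trial's main conclusions.

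**What to change.** In SAP Table RHBX.6.4 and Appendix 4, add a rule for a joint made nonevaluable by an on-study intra-articular injection:
- Carry that joint's last pre-injection status forward into later TJC and SJC, separately for tenderness and for swelling. A joint that was tender but never swollen must not become a swollen joint.
- After injection of a joint that was tender at its last pre-injection assessment, do not count the patient as a TJC = 0 responder. Apply the same rule to SJC = 0 if the joint was swollen.
- Keep proration over evaluable joints for joints excluded at screening.

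The cost is a few sentences and a programming flag, because the injected joint and drug are already recorded in the eCRF. No clinical rule changes. The downside is that an injected joint that would have resolved anyway is counted as active; the current rule can be kept as a sensitivity analysis to show how much this matters. One gap remains: a joint that becomes active and is injected between two scheduled counts carries forward its earlier inactive status. Reporting the number of injected patients by arm would show whether any of this is material.
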